#### 6.3. Exploratory Efficacy Endpoints

#### 6.5. Changes to Efficacy Analysis

Analyses of the endpoints change from baseline in LOXL2, CK18, serum cytokines and metabolic profiles, LPS, procalcitonin, and ASK-1 pathways will be described in a separate biomarker analysis plan (BAP).

Fasting lipid tests (total cholesterol, HDL, LDL, VLDL), and triglycerides will not be summarized as exploratory efficacy endpoints as the requirement for fasting was removed in Amendment 2 of the protocol. In addition, Covance laboratories does not report results for cholesterol values when the sample is "icteric". As a high percentage of subjects have total bilirubin levels > 10 mg/dL for this subject population, these analyses would exclude the most severe AH subjects, and would not be representative of the entire set of subjects. The lipid profile will be summarized for safety only and insulin levels will be listed only using the same visit windows used for HbA1c.

It should also be noted that many GGT and total protein values were cancelled by Covance due to icteric samples (ie, high total bilirubin). Summaries will be presented for completeness, but it should be noted that many values, especially those at early timepoints, will be missing.

Analysis of the Chronic Liver Disease Questionnaire (CLDQ) will not be performed for the final analysis since there was no evidence of improved efficacy with treatment of SEL + PRED vs. PLA + PRED when the primary analysis was performed.

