Eligible subjects will be randomized to one of the two treatment groups. Prior to initial dosing, required Baseline/Day 1 assessments will be performed and will include vital signs, PE, HE, ascites, HRS and infection assessment, laboratory assessments, pregnancy tests (for females of child-bearing potential), and review of adverse events, concomitant medication, CLDQ questionnaire and alcohol consumption.

While on study, subjects will undergo the following procedures and laboratory assessments:

- CLDQ questionnaire at Baseline/Day 1, Weeks 4 and 24
- Sparse PK Sampling at Baseline/Day 1 and at Weeks 1, 2 and 4
- Blood for Biomarkers at Screening, Baseline/Day 1, and at Weeks 1, 2, 4, 8, 12 and 24
- Urine collection for Biomarkers at Baseline/Day 1, and at Weeks 4 and 24
- ELFTM Test and LOXL2 at Baseline/Day 1 and at Weeks 4, 12 and 24
- FibroScan (if available and in subjects without ascites) at Baseline/Day 1 and at Weeks 4 and 24
- 12-lead ECGs at Screening, Baseline/Day 1, and at Weeks 4 and 8

[figure not shown]
Treatment will be administered for 28 days inclusive of inpatient, and if applicable, outpatient periods.
Up to 60 subjects per arm will be randomized in order to obtain 50 subjects in each arm for the full analysis set (ie, subjects randomized with histologically-proven severe AH who took at least one dose of study drug)
 Treatment Group B: GS-4997 placebo (1 tablet) AND prednisolone 40 mg (4 x 10 mg tablets) administered orally once daily; n=50-60 subjects
• Treatment Group A: GS-4997 18 mg (1 x 18 mg tablet) AND prednisolone 40 mg (4 x 10 mg tablets) both administered orally once daily; n=50-60 subjects
PPD
Intensive PK Sub-study
• Stool collection at Baseline/Day 1 and at Weeks 4 and 24.
 Urine collection at Screening (for drug screen, pregnancy screen, and to rule out infection)
• Hemoglobin A1c at Baseline/Day 1 and at Weeks 12, and 24
 Blood glucose, insulin and lipid profile at Screening, Baseline/Day 1 and at Weeks 4, 12 and 24

Criteria for Evaluation:

Cafatan	Cafate will be avaluated by avamining the insidence of treatment
Safety:	Safety will be evaluated by examining the incidence of treatment emergent adverse events, including serious adverse events, clinical laboratory tests, ECGs, and vital signs.

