6.9.4. Quality of Life (QoL) Measures

The Chronic Liver Disease Questionnaire (CLDQ) will be collected at Baseline/Day 1, Week 4, and Week 24. It is recommended to administer this questionnaire prior to the clinical and laboratory assessments. Legally Authorized Representative may assist the subject in completing the questionnaires. If the subject is unable or refuses to complete a questionnaire, this should be documented on the relevant eCRF. The CLDQ asks 29 questions related to liver disease to measure health related quality of life in subjects with chronic liver disease.

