# 1. INTRODUCTION

This statistical analysis plan (SAP) describes the statistical analysis methods and data presentations to be used in tables, figures, and listings (TFLs) for the final analysis for Study GS-US-416-2124 which will be conducted after all subjects complete their Week 24 study visit and/or Week 24 subject status form or prematurely discontinue from study. This SAP is based on Amendment 3 of the study protocol dated 04 August 2017 and the electronic case report form (eCRF). The SAP will be finalized before the database is finalized. Any changes made after the finalization of the SAP will be documented in the clinical study report (CSR).

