## 2.2. Internal Administrative Interim Analysis

An administrative interim analysis of efficacy and safety data was performed by the external statistician and reviewed by 2 individuals from Gilead. The purpose of this analysis was to assess the efficacy and safety of selonsertib + prednisolone in alcoholic hepatitis to support further planning and development of selonsertib for this indication. The 2 unblinded individuals from Gilead were independent of the GS-US-416-2124 study team and were not directly involved in routine study conduct. Individuals from Gilead who were unblinded were documented on an unblinding form, and the rationale for performing the internal interim analysis was documented per Gilead standard operating procedures. The Study Team remained blinded to treatment assignment until after the primary analysis (ie, all subjects had completed through the later of their Week 8 study visit, last dose date plus 30 days, or prematurely terminated from study) database had been finalized and the study was unblinded for the primary analysis.

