# 2.3. Primary Analysis

The primary analysis was conducted once all subjects completed the later of their safety followup visit 30 days following their last dose of study drug or Week 8 study visit; or they prematurely terminated from study. All data collected with onset/visit dates on/prior to 16 February 2018 (the date the last subject completed their Week 8 visit) were included in the database snapshot for the primary analysis. All outstanding data queries were resolved or adjudicated as unresolvable, and the data was cleaned and finalized. Treatment assignments were unblinded and TFLs were displayed by treatment group.

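### The CLDQ quality-of-life analysis is omitted from the final analysis, and the only reason given is the unblinded between-arm efficacy result

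*SAP*

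**What the plan says.** **Collection.** Protocol 6.9.4 states: "The Chronic Liver Disease Questionnaire (CLDQ) will be collected at Baseline/Day 1, Week 4, and Week 24". The protocol synopsis gives the same schedule ("CLDQ questionnaire at Baseline/Day 1, Weeks 4 and 24"), as do the visit sections (6.2.2, 6.3.4, 6.5.3) and the Appendix 2 procedures table.

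**Omission.** SAP 6.5 states that CLDQ analysis "will not be performed for the final analysis since there was no evidence of improved efficacy with treatment of SEL + PRED". The same sentence then names the comparator and the occasion on which this was found: "vs. PLA + PRED when the primary analysis was performed".

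**What was known by then.** SAP 2.3 dates the primary-analysis data cut to "16 February 2018 (the date the last subject completed their Week 8 visit") and adds: "Treatment assignments were unblinded and TFLs were displayed by treatment group". SAP 2.2 confirms the change in blinding status: "The Study Team remained blinded to treatment assignment until after the primary analysis" database had been finalised.

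**What this SAP governs.** SAP 1 says it covers the final analysis, "which will be conducted after all subjects complete their Week 24 study visit and/or Week 24 subject status form" or leave the study early.

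**The concern.** An analysis can properly be dropped for reasons unrelated to the treatment comparison, such as an assay that failed or a form that was not completed. Here the stated reason is the treatment comparison itself. Under that rule, the wording implies that the questionnaire would have been reported had the drug looked effective, and it goes unreported because the drug did not. That is outcome-dependent reporting, whatever the intent.

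What is at stake is modest but real. A null result on efficacy does not show that quality of life was the same in both arms. A difference in CLDQ score in either direction would be absent from the final outputs. Subjects, or their representatives, were also asked to complete a 29-item form at up to three visits, and the final analysis would not use it.

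**Working it through.** There is no planned figure to reproduce and no power or error rate to recompute. The check is one of timing, stated reason and consistency.

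**1. Was the decision taken with knowledge of the arms?** SAP 6.5 cites a finding from the primary analysis. SAP 2.3 says that analysis was run unblinded, by treatment group. The reason could not have been available before unblinding.

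**2. Which questionnaires were due by then?** The cut was the date of the last subject's Week 8 visit, 16 February 2018. Every scheduled Baseline and Week 4 CLDQ visit had therefore passed. For that last subject, Week 24 falls 24 − 8 = 16 weeks later: 16 × 7 = 112 days, or about 8 June 2018 before visit windows. Some Week 24 forms could still have been outstanding at the cut, but all would be due before the final analysis.

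**3. Is another reason offered?** No. The reasons in SAP 6.5 compare as follows:

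| Measure | Reason given | What is still produced |
|---|---|---|
| LOXL2, CK18, cytokines and similar | Covered by a separate biomarker plan | Reported there |
| Fasting lipids | Fasting requirement removed; icteric samples not resulted | Safety summary |
| Insulin | None specific to insulin | Listing |
| GGT, total protein | Many values cancelled | Still summarised |
| CLDQ | No efficacy at the primary analysis | Nothing |

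**4. Is the efficacy reason applied elsewhere?** Not in the visible text. Appendix 1 keeps by-visit tables, in both the FAS and the mITT set, for ELF and its components (Tables 15.9.3.1.1 to 15.9.3.1.8) and alcohol recidivism (15.9.3.2.1 and 15.9.3.2.2). It also keeps HbA1c tables in both sets (15.9.3.3.1 and 15.9.3.3.2). Lack of efficacy would argue equally against all of these. FibroScan has no Appendix 1 output either, but the visible SAP gives no reason, so it is not evidence on this point.

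**5. Is there a substitute for the CLDQ?** AUDIT and SADQ are completed at Screening only and measure alcohol use and dependence. Alcohol consumption is assessed at follow-up visits but is not quality of life. The CLDQ is the only quality-of-life instrument in the schedule.

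**6. How much data is involved?** At the recruitment target of 100 FAS subjects, the ceiling is 100 × 3 = 300 questionnaires. The true number will be lower because of death, transplant, withdrawal, and subjects unable or unwilling to complete the form, which Protocol 6.9.4 allows for.

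**The case against.** The best defence is that the change is declared openly, with its reason, under a heading made for that purpose. The CLDQ is in none of the visible primary or secondary endpoints (Protocol 8.1.1 and 8.2, SAP 6.1), so it appears to be exploratory. In a severe disease with high mortality, a Week 24 questionnaire describes a selected group of survivors and may say little about the drug. All of that stands, and it limits the weight of the point. It does not supply a reason independent of the result, and incomplete data call for completion counts rather than omission.

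Several stronger readings are tempting, and the documents do not support them:

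- **An unfavourable CLDQ result was suppressed.** The stated trigger is efficacy in general. Nothing says CLDQ scores had been looked at.
- **The primary objective is compromised.** Protocol 8.1.1 evaluates safety and tolerability through adverse events, laboratory tests, ECGs, vital signs and discontinuations for adverse events. The CLDQ is not listed.
- **Harm would go undetected.** A worsening in CLDQ score would be missing from the final outputs. Clinical deterioration would still appear in the adverse-event, Child-Pugh, hepatorenal syndrome, infection, transplant and death outputs.
- **The only patient-reported information is lost.** Alcohol consumption is also followed over time, and may rest on subject report. The supportable description of the CLDQ is the only quality-of-life instrument.
- **No CLDQ result exists in any analysis.** SAP 6.5 speaks of the final analysis. The primary-analysis outputs are not in these documents, and Baseline and Week 4 summaries may have been produced then.
- **A specified analysis was broken off.** The exploratory objectives and endpoints are withheld. The readable protocol text commits to collecting the CLDQ, but no CLDQ analysis method can be read.

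**Conclusion.** The point holds in limited form. The final analysis omits the only quality-of-life instrument for a reason that is, in the SAP's own words, the unblinded between-arm efficacy result. Reporting of this outcome is therefore conditional on the result. The size is one outcome at three scheduled time points, absent from the final-analysis outputs. The direction and amount of any resulting bias are unknown.

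The conclusion rests on the stated reason being the complete one, and on Appendix 1 being the full list of final outputs. The exploratory status of the CLDQ is inferred from its absence elsewhere and from the heading of SAP 6.5. The omission should be corrected, but it does not threaten the primary safety assessment.

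**What to change.** Replace the CLDQ sentence in SAP 6.5. Simply deleting it would erase the only record that the decision followed unblinding. The replacement should commit to:

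- CLDQ score and change from baseline, summarised by arm at Baseline, Week 4 and Week 24, on observed cases;
- at each visit, the number in each arm who completed the form, did not complete it, had died, or had been transplanted (SAP 6 already excludes post-transplant data from efficacy analyses);
- a by-subject listing;
- a label of exploratory and descriptive, with no hypothesis test.

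State the scoring and missing-item rules and a visit window, since none for the CLDQ is visible in the SAP. Add the outputs to Appendix 1. In the CSR, say that the omission was decided after unblinding and then reversed, and note that Week 24 results reflect survivors able to complete the form.

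The cost is small: one or two tables, one listing and the scoring derivation, all from scheduled data. No new visits, subjects or tests are needed.

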# 7. SAFETY ANALYSES

#### 7.1. Adverse Events and Deaths

#### 7.1.1. Adverse Event Dictionary

Clinical and laboratory adverse events (AEs) will be coded using the current version of MedDRA. System organ class (SOC), HLGT, high-level term (HLT), preferred term (PT), and lower-level term LLT will be provided in the AE dataset.

#### 7.1.2. Adverse Event Severity

Adverse events are graded by the investigator as Grade 1, 2, 3, 4, or 5 according to Common Terminology Criteria for Adverse Events (CTCAE) version 4.03. The severity grade of events for which the investigator did not record severity will be categorized as "missing" for tabular summaries and data listings, and the most severe event will be considered in data presentations.

#### 7.1.3. Relationship of Adverse Events to Study Drug

Related AEs are those for which the investigator selected "Related" on the AE eCRF to the question of "Related to Study Treatment." Events for which the investigator did not record relationship to study drug will be considered related to study drug for summary purposes. However, by-subject data listings will show the relationship as missing.

#### 7.1.4. Serious Adverse Events

Serious adverse events (SAEs) will be identified and captured as SAEs if AEs meet the definition of an SAE specified in the study protocol. SAEs captured and stored in the clinical database will be reconciled with the SAE database from the Gilead Pharmacovigilence and Epidemiology Department before data finalization.

#### 7.1.5. Treatment-Emergent Adverse Events

7.1.5.1. Definition of Treatment-Emergent Adverse Events

Treatment-emergent adverse events (TEAEs) are defined as 1 or both of the following:

- Any AEs with an onset date on or after the study drug start date and no later than 30 days after permanent discontinuation of study drug
- Any AEs leading to premature discontinuation of study drug.

#### 7.1.5.2. Incomplete Dates

If the onset date of the AE is incomplete and the AE stop date is not prior to the first dosing date of study drug, then the month and year (or year alone if month is not recorded) of onset determine whether an AE is treatment emergent. The event is considered treatment emergent if both of the following 2 criteria are met:

- The AE onset is the same as or after the month and year (or year) of the first dosing date of study drug, and
- The AE onset date is the same as or before the month and year (or year) of the date corresponding to 30 days after the date of the last dose of any study drug

An AE with completely missing onset and stop dates, or with the onset date missing and a stop date later than the first dosing date of study drug, will be considered to be treatment emergent. In addition, an AE with the onset date missing and incomplete stop date with the same or later month and year (or year alone if month is not recorded) as the first dosing date of study drug will be considered treatment emergent.

- All AEs recorded between screening and prior to first dose of study drug
- All SAEs with an outcome of death

Multiple events reported within an SOC or PT will be counted once only per subject in each summary. Adverse events will be summarized by treatment group and will be listed first in alphabetic order of SOC and then by PT in descending total frequency within each SOC. In summaries by severity grade, the most severe grade will be used for those AEs that occurred more than once in an individual subject during the study.

In addition to the above summary tables, the following AEs will be summarized by treatment group and PT only:

- All TEAEs (occurring in  $\geq 10\%$  of subjects within any group)
- TE treatment-related AEs (occurring in  $\geq$  5% of subjects within any group)
- Grade 3 or Higher TE AEs
- Grade 3 or Higher TE treatment-related AEs

- Grade 3 or Higher TE treatment-related AEs Leading to Premature Discontinuation of Selonsertib/Placebo
- TE SAEs
- TE treatment-related SAEs

The sort order for these tables will be in descending order of total frequency of PT events and alphabetic order of PT for events with the same total frequency.

At the request of the Pharmacovigilence and Epidemiology group, the following AE tables will be produced to summarize by treatment group, SOC, HLT and PT:

- All TE AEs
- TE SAEs

The sort order for these tables will be in descending order of total frequency of HLT and PT events and alphabetic order for SOC.

In addition, data listings will be provided for the following:

- All AEs, indicating whether the event is treatment emergent
- All AEs of Grade 3 or higher
- All AEs of Grade 3 or higher related to study treatment
- SAEs
- SAEs related to study treatment
- Deaths
- All AEs leading to death
- AEs leading to discontinuation of any of the study drugs
- AEs leading to dose modification or interruption of any of the study drugs

#### 7.1.7. Analysis of Adverse Events of Interest

Post-baseline criteria (up to last dose date of SEL/PLA [confirmatory values may be collected after the last dose date]) will be used to screen for individual subjects who should stop dosing with SEL/PLA study drug. DMC members used these same criteria to determine whether there was a > 20% higher percentage of subjects in the SEL + PRED group than PLA + PRED group with events in any of the 4 categories (ie, DMC trial stopping criteria).

SEL/PLA study drug stopping criteria for an individual subject is as follows:

- 1) Grade 3 or higher, treatment-emergent, treatment-related adverse event(s) of a specific type (excluding evaluation of liver function) that leads to discontinuation of SEL/PLA
- 2) Death on/prior to Study Day 28
- 3) Lille Score > 0.85 while on study drug
- 4) Any of the post-baseline SEL/PLA laboratory stopping criteria:
  - ALT or AST > 500 U/L
  - ALT or  $AST > 5 \times Baseline/Day 1$  (confirmed on repeat testing)
  - Total Bilirubin > 3 x Baseline/Day 1 or Nadir (confirmed on repeat testing)

The baseline/Day 1 value will be defined as the last available measurement on/prior to first dose of SEL/PLA, and the nadir value will be defined as the lowest postbaseline value prior to the current value being assessed. A listing will be provided that includes each individual subject who met any of the SEL/PLA stopping criteria.

Prednisolone study drug stopping criteria in an individual subject is as follows: Subjects with a Week 1 Lille score  $\ge 0.56$  will be prematurely discontinued from PRED. This criteria is the same as the secondary efficacy parameter Lille null response (Lille score  $\ge 0.56$  at Week 1) which is described in Section 6.2.4 of this SAP.

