7.5. Toxicity Management

Treatment-emergent toxicities will be noted by the Investigator and brought to the attention of the Medical Monitor. Whether or not considered treatment-related, all subjects experiencing AEs must be monitored periodically until symptoms subside, any abnormal laboratory values have resolved or returned to baseline levels or they are considered irreversible, or until there is a satisfactory explanation for the changes observed.

Administration of all study drugs may be discontinued due to a clinical or laboratory adverse event. Subjects are allowed to take one study drug and not the other.

Prednisolone may be dose-reduced or interrupted at the discretion of the investigator (e.g. due to new-onset, severe sepsis or diabetes mellitus that cannot adequately be controlled). Prednisolone should be discontinued in subjects with a Lille Score ≥ 0.56 at Day 7 (null responders); these subjects may continue GS-4997/placebo treatment. Except in Lille Score null responders, restarting prednisolone may be considered if the reason for interruption has resolved or become adequately controlled in the opinion of the investigator within 7 days of prednisolone interruption. Any decision to restart prednisolone must be reviewed with the Medical Monitor.

There is no option for GS-4997/placebo dose reduction, but GS-4997/placebo may be interrupted due to drug-related toxicity (see below). If GS-4997/placebo is interrupted, it may be restarted on

a case by case basis if the reason for interruption has resolved or become adequately controlled in the opinion of the investigator within 7 days of GS-4997/placebo interruption. Any decision to discontinue or restart GS-4997/placebo must be reviewed with the Medical Monitor.

Subjects who meet any of the following criteria must stop GS-4997/placebo

- Laboratory Criteria (based on central laboratory data):
 - Total bilirubin > 3x Baseline/Day 1 or nadir (confirmed by immediate repeat testing)
 - ALT and/or AST > 5x Baseline/Day 1 (confirmed by immediate repeat testing), unless the elevation is thought by the Principal Investigator to be secondary to an etiology other than GS-4997-related, drug-induced liver injury (e.g. infection).

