 - AST and/or ALT >500 U/L should trigger prompt (within 24-48 hours) evaluation of patients for consideration of GS-4997/placebo discontinuation. If patients with AST and/or ALT >500 U/L are continued on study drug, they must be monitored closely with repeat PE and laboratory evaluation at least 3 times per week.
- Lille score > 0.85 at any time point (eg, on/after first scheduled post-Baseline/Day 1 visit) while on study drug (base on central or local laboratory data)
- Any Grade 3 or higher AE assessed as possibly or likely related to GS-4997

Other than in the case of the liver enzymes noted above, Grade 3 or 4 clinically significant laboratory abnormalities should be confirmed by repeat testing as soon as practical to do so (Medical Monitor needs to be notified), and preferably within 3 calendar days of receipt of the original test results.

Clinical events and clinically significant laboratory abnormalities will be graded according to the Common Terminology Criteria for Adverse Events (CTCAE) Version 4.03, which can be found at http://evs.nci.nih.gov/ftp1/CTCAE/CTCAE_4.03_2010-06-14_QuickReference_8.5x11.pdf.

When restarting investigational medicinal product following resolution of the adverse event, the investigational medicinal product should be restarted at full dose following discussion with the Medical Monitor.

Any questions regarding toxicity management should be directed to the Medical Monitor.

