8.11. Data Monitoring Committee

An independent, external Data Monitoring Committee (DMC) that includes two hepatologists and a PhD statistician will convene prior to study start, once 20 subjects have been treated for 28 days and every 3 months thereafter to monitor the study for safety events including SAEs, death, premature discontinuation of treatment for AEs, Grade 3 and higher AEs, Grade 3 and higher treatment-emergent laboratory abnormalities, and individual subject stopping criteria for GS-4997/placebo study drug (see Section 7.5). The DMC will also evaluate (based on an unblinded review of safety data) and recommend early termination of the trial if there is a > 20% higher percentage of subjects in the GS-4997/prednisolone group than in the prednisolone alone group with: 1) Grade 3 or higher, treatment-emergent, treatment-related adverse event(s) of a specific type (excluding evaluation of liver function) where GS-4997/Placebo was prematurely withdrawn; 2) death on/prior to Study Day 28; 3) Lille score > 0.85 while on study drug; 4) any of the post-baseline GS-4997/placebo laboratory stopping criteria (ie, ALT or AST > 500 U/L that led to discontinuation of GS-4997/placebo, ALT or AST > 5x Baseline/Day 1 [confirmed on repeat testing]; or total bilirubin > 3 x Baseline/Day 1 or nadir [confirmed on repeat testing]).

The DMC will provide recommendations to Gilead on whether the nature, frequency, and severity of adverse effects associated with study treatment warrant the early termination of the study in the best interest of the participants, whether the study should continue as planned, or the study should continue with modifications. The DMC may also provide recommendations as needed regarding study design.

The DMC's specific activities will be defined by a mutually agreed charter, which will define the DMC's membership, conduct and meeting schedule.

While the DMC will be asked to advise Gilead regarding future conduct of the study, including possible early study termination, Gilead retains final decision-making authority on all aspects of the study.

9. **RESPONSIBILITIES**

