# 2. TYPE OF PLANNED ANALYSIS

# 2.1. Data Monitoring Committee Analyses

An independent external Data Monitoring Committee (DMC) that included 2 hepatologists and a PhD statistician convened prior to study start, once 20 subjects had completed Study Day 28, and every 3 months thereafter to review the progress of the study and perform interim reviews of safety data in order to protect subject welfare and preserve study integrity.

The DMC additionally evaluated trial stopping criteria, based on an unblinded review of safety data, and recommend early termination of the trial if there was a > 20% higher percentage of subjects in the SEL + PRED group than in the PLA + PRED group with: 1) Grade 3 or higher treatment-emergent, treatment-related adverse event(s) of a specified type, excluding evaluation of liver function, that led to premature discontinuation of selonsertib/placebo; 2) Death on/prior to Study Day 28; 3) Lille score > 0.85 while on study drug; or 4) post-baseline selonsertib/placebo laboratory stopping criteria (ie, ALT or AST > 500 U/L, ALT or AST > 5 x baseline [confirmed on repeat testing], and/or total bilirubin > 3 x baseline or nadir [confirmed on repeat testing]). See Section 7.1.7 of this SAP.

The DMC was to recommend to the sponsor whether the nature, frequency, and severity of adverse effects associated with study treatment warranted the early termination of the study in the best interests of the participants, whether the study should continue as planned, or whether the study should continue with modifications.

The DMC's roles and responsibilities and the scope of analysis provided to the DMC were provided in a mutually agreed upon charter, which defined the DMC membership, meeting logistics, and meeting frequency.

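### SAP 7.1.7 presents the DMC's between-arm criteria as individual stopping rules and drops the discontinuation condition on ALT/AST > 500 U/L

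*SAP*

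**What the plan says.** The protocol has two rule sets. Section 7.5 governs the individual patient: "Subjects who meet any of the following criteria must stop GS-4997/placebo". Section 8.11 governs the trial: the DMC is to recommend termination if the percentage of subjects in any of four categories is more than 20% higher on GS-4997 than on control. Section 8.11 keeps them apart. It lists the individual criteria, with a reference to 7.5, among the things the DMC monitors, and then says the DMC will in addition evaluate the between-arm criteria.

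SAP 7.1.7 works with one list. It says the criteria "will be used to screen for individual subjects who should stop dosing with SEL/PLA study drug", and then that "DMC members used these same criteria to determine whether there was a > 20% higher percentage of subjects" in the selonsertib arm, describing them in brackets as the DMC trial stopping criteria. The list itself is headed "SEL/PLA study drug stopping criteria for an individual subject is as follows". The section promises a listing of subjects who met any criterion. Appendix 1 adds Table 15.11.2.4.2 (any SEL/PLA stopping criterion), Table 15.11.2.4.4 (SEL/PLA laboratory stopping criteria) and Listings 16.2.7.6.1 to 16.2.7.6.4.3, one for each criterion.

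**The concern.** Safety is the primary objective. A table titled as subjects meeting a SEL/PLA stopping criterion will be read as the number who reached the point at which the protocol required the drug to stop. If the list behind it is a different one, the table answers a different question.

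One laboratory item raises a second problem. Protocol 7.5 lets a subject with ALT or AST above 500 U/L continue under close monitoring, and Protocol 8.11 counts such a subject only if the drug was in fact discontinued. A list without that condition records a permitted continuation as a stopping event, under either protocol section.

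**Working it through.** No calculation in the plan needs reproducing. The check sets the three lists side by side.

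| Item | Protocol 7.5 (individual) | Protocol 8.11 (DMC) | SAP 7.1.7 |
|---|---|---|---|
| Related AE, Grade 3 or higher | "Any Grade 3 or higher AE assessed as possibly or likely related to GS-4997" | Specific type, liver function excluded, and "where GS-4997/Placebo was prematurely withdrawn" | As 8.11 |
| Death by Day 28 | Absent | Present | Present |
| Lille score > 0.85 on drug | Present | Present | Present |
| Bilirubin > 3x baseline or nadir, confirmed | Present | Present | Present |
| ALT/AST > 5x baseline, confirmed | Present, with an exemption if the investigator finds another cause | Present, no exemption | As 8.11 |
| ALT/AST > 500 U/L | Triggers evaluation; dosing may continue under monitoring | "ALT or AST > 500 U/L that led to discontinuation of GS-4997/placebo" | Unconditional |

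**Which list is it?** The four SAP categories are those of 8.11, in the same order. The AE and death rows do not match 7.5. Death cannot identify a subject who ought to stop dosing. An AE item that requires the drug to have been stopped already cannot find a subject who met 7.5 and was not stopped. The individual-subject heading is therefore wrong.

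**Does it match 8.11?** In every row but the last. SAP 2.1 restates the DMC rule with the same omission: "ALT or AST > 500 U/L, ALT or AST > 5 x baseline [confirmed on repeat testing". Listing 16.2.7.6.4.2 is titled without the condition too.

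**Is there another version within the SAP?** Yes. SAP 4.2.2, on adherence, describes individual SEL/PLA stopping criteria without death and without the non-liver restriction, and applies them only to subjects who discontinued SEL/PLA early. That serves adherence only and does not restore the condition for the safety outputs.

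**Can the > 500 U/L item matter on its own, or does the 5x item absorb it?** 500 / 5 = 100, so a subject whose baseline is above 100 U/L passes 500 U/L before reaching 5x. Screening admits AST from 50 to 400 U/L, and from 400 U/L a rise of just over 500 / 400 = 1.25-fold is enough. The item is not redundant.

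**Direction and scale.** Relative to 8.11, dropping the condition can only add subjects to the > 500 U/L row, namely those who stayed on SEL/PLA. It adds to an any-criterion count only those who met no other criterion. The between-arm difference can move either way. One subject is 1/50 = 2.0 or 1/60 = 1.7 percentage points of an arm at the planned 50 to 60 per group.

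**The case against.** Several points on the other side stand.

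- The SAP hides nothing. SAP 7.1.7 calls these the DMC trial stopping criteria, and SAP 2.1 refers to 7.1.7. The labelling fault is one imprecise heading.
- The protocol invites some of the confusion. Section 7.5 places the 500 U/L item under its mandatory-stop heading, and 8.11 calls its own laboratory items stopping criteria and states the 5x item without the exemption. The missing exemption is therefore no departure from 8.11.
- The shells of Tables 15.11.2.4.2 and 15.11.2.4.4 are not in the documents. That they use the 7.1.7 list is inferred from their titles and from the matching listings.
- The events can be found elsewhere. Related Grade 3 or higher AEs, whatever the action taken, are in Tables 15.11.2.3.2.1 and 15.11.2.3.2.2 and Listing 16.2.7.4.2. SEL/PLA discontinuations and interruptions are in Tables 15.11.5.1 and 15.11.5.4. Each criterion has its own listing.

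A reader might infer two stronger charges. The first is that the DMC applied the wrong rule. SAP 2.1 does restate the rule without the condition, but the DMC's working rules are in a charter that is not among the documents and may contain it. The SAP describes the DMC's evaluations in the past tense, so this output cannot change them. The second is that SAP 7.7 is false in declaring no deviation from the protocol-specified safety analyses. Protocol 8.8 specifies no table of subjects meeting stopping criteria, and 7.5 and 8.11 are dosing and monitoring rules, so that charge is not made out.

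What survives is the heading and the missing condition, both plain on the text.

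**Conclusion.** The point holds in a limited form. SAP 7.1.7 labels the Protocol 8.11 DMC list as an individual-subject rule, and SAP 7.1.7 and 2.1 omit 8.11's condition on ALT/AST above 500 U/L. Followed exactly, the SAP would count subjects who continued dosing as the protocol allows among those meeting a stopping criterion.

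The consequence is confined to descriptive safety output; no estimate or test changes. The documents do not say how many subjects exceeded 500 U/L and stayed on SEL/PLA, and the number may be zero. The finding for Listing 16.2.7.6.4.2 rests on its title and the SAP text. For the two tables it assumes that they use the 7.1.7 list. The documents do not support reading this as evidence that the DMC erred or that adverse events go unreported.

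**What to change.** 1. Retitle the SAP 7.1.7 list, Tables 15.11.2.4.2 and 15.11.2.4.4 and the supporting listings as the DMC criteria of Protocol 8.11.
2. In SAP 7.1.7 and 2.1, restore the condition that ALT/AST above 500 U/L counts only if SEL/PLA was discontinued because of it. If the DMC in fact used the unconditional form, say so instead.
3. Split the > 500 U/L row by SEL/PLA stopped or continued, so that either definition can be read from the table.
4. Note the correction as made after the primary-analysis unblinding described in SAP 2.3.

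A separate table of the Protocol 7.5 criteria is optional, since the protocol does not ask for one. If it is made, a footnote should say that relatedness under SAP 7.1.3 is to study treatment and may include events attributed to prednisolone, whereas 7.5 refers to GS-4997.

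The cost is a few lines of SAP text and minor programming. No dosing rule or DMC rule changes.
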